11.4.2.2 Derivations and Handling of Missing Baseline Data

Definition	Reporting Details
Change from Saline ¹	=Highest Challenge Value – Highest Saline Value
% Change from Saline ¹	= $100 \times [(Highest\ Challenge\ Value - Highest\ Saline\ Value) / Highest\ Saline\ Value]$
% Attenuation of Reference Response	= $100 \times [1 - (Test\ Mean / Reference\ Mean)]$
Change from Baseline	= Post-Dose Visit Value – Baseline
% Change from Baseline	= $100 \times [(Post-Dose\ Visit\ Value - Baseline) / Baseline]$
Maximum Change from Baseline	= Calculate the change from baseline at each given time point and determine the maximum change

NOTES :

- Unless otherwise specified, the baseline definitions specified in Section 11.4.2.1 Baseline Definitions will be used for derivations for endpoints / parameters and indicated on summaries and listings.
- Unless otherwise stated, if baseline data is missing no derivation will be performed and will be set to missing.
- The baseline definition should be footnoted on all change from baseline displays.

1. Example of calculations of Change and % Change from Saline in the BAC:

Challenge concentration (squ/mL)	Planned relative time	FEV1 (L)	FEV1 Change		
			Max FEV1 (L)	from Max Saline (L)	(%)
45250	Saline	2 M	3.79	4.02	
		3 M	4.02		
		4 M	3.83		
		5 M	4.11	4.11	2.2
		10 M	4.08	4.08	0.06 1.5
		15 M	3.86	3.86	-0.16 -4.0
		20 M	3.97	3.97	-0.05 -1.2
		30 M	4.16	4.16	0.14 3.5
		45 M	4.12	4.12	0.10 2.5
	1 H-READ 1		4.14	4.14	0.12 3.0
	1 H-READ 2		3.76		

11.4.2.3 Imputation for Values Below and Above Limit of Quantification

PD responses which are below the assay's respective lower limit of quantification (LLQ) will be imputed using half of the LLQ value.

PD responses which are above the assay's respective upper limit of quantification (ULQ) will be imputed using the ULQ value.

In the event that multiple LLQ/ULQ values are present the minimum for that analyte (for LLQ) and maximum for that analyte (ULQ) should be used in the imputations. If any LLQ values are zero then a suitable small constant may be used in place, to allow the data to be log transformed (for example half of the smallest observed non-zero value).

11.4.3 Reporting Process & Standards

Reporting Process			
Software			

 The currently supported versions of SAS and S-Plus software will be used. 			
Reporting Area			
HARP Server	uk1salx00175		
HARP Area*	\arprod\gsk2245035\mid205540\final (for CSR) \arprod\gsk2245035\mid205540\headline (for Headline Results) \arprod\gsk2245035\mid205540\interim (for Interim Analysis)		
QC Spreadsheet	\arwork\gsk2245035\mid205540\final\documents (for CSR) \arwork\gsk2245035\mid205540\headline\documents (for Headline Results) \arwork\gsk2245035\mid205540\interim\documents (for Interim Analysis)		
*=upcoming functionality change in HARP v7 may impose naming conventions which would supersede these suggestions for reporting effort names			
Analysis Datasets			

 Analysis datasets will be created according to Legacy GSK A&R dataset standards 			
Intermediate Datasets			

 The Bayesian framework necessitates the storage of intermediate outputs datasets (convention dictates that they be stored in the dddata folder of the reporting effort). It is strongly recommended that a file naming convention be adopted across all MCMC analyses to allow easy grouping/location of associated items. The naming convention has to follow the SAS dataset length rules, and any HARP naming conventions imposed in the upcoming v7 release and existing limitations on special characters, but the following is proposed (it may be modified as necessary/appropriate): The file name is made up of components joined by underscores. This should allow items to automatically group/sort when viewed as a list. 			
Component ID	Description	Examples	Clarification
1	Three letters aligning item to its closest study objective	BAC NAC TL7	Bronchial Allergen Challenge Nasal Allergen Challenge Target engagement

Reporting Process			
		IDX	Intradermal Challenge
2	Single letter if the response variable was Univariate or Multivariate	U M	Univariate Multivariate
3	Three letters for the sample matrix	FEV SPU NLS NLF SRM	FEV1 (Lung data) Sputum Nasal Lavage Fluid Nasal Lavage Filters Serum
4	Up to 5 letters for the Item/Analyte (can exceed 5 if BICATCD values are longer)	LARWM LARMI EARWM EARMI <Bicat code>	LAR WM 4-10h CFB FEV1 LAR Min CFB FEV1 EAR WM 0-2h CFB FEV1 EAR Min CFB FEV1 <Taken from SI.BIOMARK and/or dataset manager>
5	Single digit Population code	1 2 3 4 etc	All Subjects Per Protocol mITT Sputum Producers (Statistician will need to track assignments)
6	Single digit Model ID (may vary depending on the analysis, so model 1 can have different meanings across objectives/sample matrices/endpoints)	1 2 etc	Pre-BAC Samples only All BAC Samples (Statistician will need to track assignments on a per objectives/sample matrices/endpoint basis)
7	Double digit Analysis ID (specific to the modelling, can be used to store the R1-R3 outputs and models fitted whilst covariate building or the models with informative priors)	01 02 03 04 etc	Statistician will need to track on a per item basis
8	MCMC related item	dsetin poall pokdein + Others as required	The dataset that was passed to MCMC Posterior Summary Stats (processed and ready for display) Posterior samples

• Example for the input dataset passed to PROC MCMC for the Primary analysis of LAR WM4-10h CFB Saline Baseline using the PP population (analysis ID 01):

Reporting Process
“BAC_U_FEV_LARWM_2_1_01_dsetin”

 Example for the Output statistics (Medians and credible intervals) for the Background samples of Nasal Lavage IL-5 using the All Subjects population: “NAC_U_NLS_IL5_1_1_01_poall” The above naming convention (excluding item 8) can also be used to name the respective reporting effort SAS programs / macros that implement the different analyses
Generation of RTF Files

 RTF files will be generated for all reporting efforts.
Reporting Standards
General

 The current GSK Integrated Data Standards Library (IDSL) will be applied for reporting, unless otherwise stated: 
 4.03 to 4.23: General Principles 5.01 to 5.08: Principles Related to Data Listings 6.01 to 6.11: Principles Related to Summary Tables 7.01 to 7.13: Principles Related to Graphics
Formats

 All data will be reported according to the actual treatment the subject received unless otherwise stated. GSK IDSL Statistical Principles (5.03 & 6.06.3) for decimal places (DP's) will be adopted for reporting of data based on the raw data collected. Numeric data will be reported at the precision collected on the eCRF. The reported precision from non eCRF sources will follow the IDSL statistical principles but may be adjusted to a clinically interpretable number of DP's.
Planned and Actual Time

 Reporting for tables, figures and formal statistical analyses : 
 Planned time relative to dosing will be used in figures, summaries, statistical analyses and calculation of any derived parameters, unless otherwise stated. The impact of any major deviation from the planned assessment times and/or scheduled visit days on the analyses and interpretation of the results will be assessed as appropriate. Reporting for Data Listings: 
 Planned and actual time relative to study drug dosing will be shown in listings (Refer to IDSL Statistical Principle 5.05.1). Unscheduled or unplanned readings will be presented within the subject's listings. Visits outside the protocol defined time-windows (i.e. recorded as protocol deviations) will be included in listings but omitted from figures, summaries and statistical analyses.

Reporting Standards								
Unscheduled Visits								

 • Unscheduled visits will not be included in summary tables. • Unscheduled visits will not be included in figures. • All unscheduled visits will be included in listings. 								
Descriptive Summary Statistics								
Continuous Data	Refer to IDSL Statistical Principle 6.06.1							
Categorical Data	N, n, frequency, %							
Reporting of Pharmacokinetic Concentration Data								
Descriptive Summary Statistics	Refer to IDSL Statistical Principle 6.06.1 Assign zero to NQ values (Refer to GUI_51487 for further details)							
Graphical Displays								

 • Refer to IDSL Statistical Principles 7.01 to 7.13. • Where possible the following colour scheme will be adopted noting that treatment comparisons against Placebo will utilise the style of GSK2245035 treatment: 								
Treatment Colour Plotting Symbol Line Style								
Placebo once weekly	Blue	Circle, Solid	Solid					
20 ng GSK2245035 i.n. once weekly	Orange	Triangle (up), Solid	Solid					
If applicable, eg individual subject profile plots, a different line style can be applied to distinguish Allergen Exposure in the Efficacy Figures.								
Treatment Allergen Exposure Strata Colour Plotting Symbol Line Style								
Placebo once weekly	Presumed	Blue	Circle, Solid	Solid				
	Unknown	Blue	Circle, Hollow	ShortDash				
20 ng GSK2245035 i.n. once weekly	Presumed	Orange	Triangle (up), Solid	Solid				
	Unknown	Orange	Triangle (up), Hollow	ShortDash				
In some displays the visits need to be distinguished, in which case the following colour scheme should be used whenever possible								

Reporting Standards			
Visit	Colour (SAS Syntax)	Plotting Symbol	Line Style
Screening Visit 1	bioy	Circle, Solid	Solid
Screening Visit 2	green	Diamond, Solid	Solid
Dosing Visit 1	pink	Circle, Solid	LongDash
Dosing Visit 2	brown	Diamond, Solid	LongDash
Dosing Visit 3	dep	HomeDown, Solid	Solid
Dosing Visit 4	lime	Square, Solid	LongDash
Dosing Visit 5	parp	Star, Solid	LongDash
Dosing Visit 6	salmon	Triangle, Solid	Solid
Dosing Visit 7	vlib	TriangleDown, Solid	Solid
Dosing Visit 8	magenta	TriangleLeft, Solid	Solid
Follow Up Visit 1	red	Star, Solid	Solid
Follow Up Visit 2	cyan	Square, Solid	Solid
Follow Up Visit 3	purple	TriangleRight, Solid	Solid
Note: If there is a need to also distinguish the allergen exposure strata then use of Solid/Hollow symbols and Solid/ShortDashed lines can be made, as in the above treatment example (with any LongDash mapping to Dot)			

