### 7.1.2. Time and Events Table – Dosing visit (DV) 1 (Day 1) – DV8 (Week 8) and Early Withdrawal Visit (EW)

Procedure	Pre-dose	Dose	Post-dose				Early- Withdrawal	Notes
		0 hour	20 mins	1 hour	12 hours	24 hours		
Outpatient visit		X				X	X	Subjects get discharged 1-2 hours after dosing.
Inclusion and exclusion criteria/eligibility review	X							Only on DV1
Diary card collection and review		X					X	Collect and review diary card at every dosing visit
AE/SAE review		X					X	
Concomitant medication review		X					X	
12-lead ECG	X			X		X	X	Perform on DV1 and DV8 only. Not required at EW if this occurs during FU
Vital signs (including temperature)	X 			X 		X 	X	 Perform on DV1-8  Perform on DV1, 4 and DV8 only. Not required at EW if this occurs during FU
Laboratory assessments (include liver chemistries, haematology, clinical chemistry and urinalysis)	X					X	X	Collect samples for laboratory assessments on DV1 and DV8, Not required at EW if this occurs during FU
Blood sample for PK analysis	X		X	X				Collect samples on DV1, DV4 and DV8
Genetic sample		X						Take one sample on any of the dosing visits after genetics consent.
FeNO measurement	X							Perform FeNO measurements pre-dose on all dosing visits 1-8
Nasal examination	X					X		Conducted pre-dose at all study visits and 24 hours post-dose on DV1, DV4 and DV8

Procedure	Pre-dose	Dose	Post-dose				Early-Withdrawal	Notes
			0 hour	20 mins	1 hour	12 hours		
Nasal lavage	X						X	Collect nasal lavage samples pre-dose and 24hrs post-dose on DV1, DV4 and DV8
Blood sample for biomarker analysis	X						X	Collect blood for serum samples and PBMC preparations pre-dose and 24 hrs post-dose on DV1 and DV8
Blood sample for RNA analysis	X 						X 	PAX-gene tubes for TLR7/AFFY chip gene expression in blood collected pre-dose on DV1  and 24 hrs after DV8 
Call RAMOS	X							Randomisation will occur is at Visit 1 via the IRT. Sites should also call RAMOS at DV5.
Dispensing of study medication	X							One device will be assigned on DV1. The second device will be assigned on DV5. All devices remain in the unit.
Study drug administration		X						All doses are administered in the unit.

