**Table 1 Protocol Required Safety Laboratory Assessments**

Laboratory Assessments	Parameters							
Haematology	Platelet Count		RBC Indices:	White Blood Cell (WBC) count with Differential:				
	Red Blood Cell (RBC) Count		Mean Corpuscular Volume (MCV)	Neutrophils				
	Hemoglobin		Mean corpuscular hemoglobin (MCH)	Lymphocytes				
	Hematocrit			Monocytes				
				Eosinophils				
				Basophils				
Clinical Chemistry 	Blood Urea Nitrogen (BUN)	Potassium	AST (SGOT)	Total and direct bilirubin				
	Creatinine	Sodium	ALT (SGPT)	Total Protein				
	Glucose	Calcium	Alkaline phosphatase	Albumin				
Routine Urinalysis	
 
Specific gravity
 
pH, glucose, protein, blood and ketones by dipstick
 
Microscopic examination (if blood or protein is abnormal)
 
							
Other Screening Tests	
 
HIV
 
Hepatitis B (HBsAg)
 
Hepatitis C (Hep C antibody)
 
FSH and estradiol (as needed in women of non-child bearing potential only)
 
Alcohol and drug screen (to include at minimum: amphetamines, barbiturates, cocaine, opiates, cannabinoids and benzodiazepines)
 
Urine hCG Pregnancy test 
 
							
NOTES :								

 
Details of Liver Chemistry Stopping Criteria and Required Actions and Follow-Up Assessments after liver stopping or monitoring event are given in Section 5.4.1 and Appendix 2.
 
Local urine testing will be standard for the protocol unless serum testing is required by local regulation or ethics committee.
 
								

All laboratory tests with values that are considered clinically significantly abnormal during participation in the study should be repeated until the values return to normal or baseline. If such values do not return to normal within a period judged reasonable by the investigator, the etiology should be identified and the sponsor notified.

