11.2 Appendix 2: Assessment Windows

11.2.1 Definitions of Assessment Windows for Analyses

Data Management are responsible for documenting and implementing the visit windows in this study. If an item is within its visit window it should be transferred to statistics and programming using the corresponding timeslicing key (items that fall outside of the window may be transferred using unscheduled timeslicing keys with the corresponding planned items containing no data). In addition this should also be captured in the protocol deviations dataset. For the purposes of AE, DRE and CRS assignments the algorithms described in Section 11.3.2 should be used.

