11.5 Appendix 5: Derived and Transformed Data

11.5.1 General

Multiple Measurements at One Time Point

 Generally, mean of the measurements will be calculated, unless replicate FEV₁ or PEF measurements exist in which case the maximum will be utilised, and used in any derivation of summary statistics but if listed, all data will be presented. If there are two values within a time window the value closest to the target day for that window will be used. If values are the same distance from the target then the mean will be taken. Subjects having both High and Low values for Normal Ranges at any post-baseline visits for safety parameters will be counted in both the High and Low categories of 'Any visit post-baseline' row of related summary tables. This will also be applicable to relevant Potential Clinical Importance summary tables.
Study Day

 Calculated as the number of days from randomisation date : 
 Ref Date = Missing → Study Day = Missing Ref Date < Randomisation Date → Study Day = Ref Date – Randomisation Date Ref Date ≥ Randomisation Date → Study Day = Ref Date – (Randomisation Date) + 1

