11.7 Appendix 7: Values of Potential Clinical Importance

11.7.1 Laboratory Values

Hematology Analyte	Effect	Relative – Low (Multipliers of LLN)	Relative – High (Multipliers of ULN)
White Blood Cell Count		0.67	1.82
Neutrophil Count		0.83	
Lymphocytes		0.81	
Hemoglobin	Male		1.03
	Female		1.13
Hematocrit	Male		1.02
	Female		1.17
Platelet Count		0.67	1.57
		Absolute – Low	Absolute – High
MCV (fL)		< 80	> 100
MCH (pg/cell)		< 25.78	> 34
Monocytes (K/mL)		< 0.1	> 0.9
Eosinophils (K/mL)		< 0	> 0.6
Basophils (K/mL)		< 0	> 0.9

Chemistry Analyte	Effect	Relative – Low (Multipliers of LLN)	Relative – High (Multipliers of ULN)
Albumin (mmol/L)		0.86	
Calcium (mmol/L)		0.91	1.06
Glucose (mmol/L)		0.71	1.41
Potassium (mmol/L)		0.86	1.10
Sodium (mmol/L)		0.96	1.03

Liver Function			
Test Analyte	Units	Category	Clinical Concern Range
ALT/SGPT	U/L	High	$\geq 2 \times \text{ULN}$
AST/SGOT	U/L	High	$\geq 2 \times \text{ULN}$
Alkaline Phosphatase	U/L	High	$\geq 2 \times \text{ULN}$
Total Bilirubin	$\mu\text{mol/L}$	High	$\geq 1.5 \times \text{ULN}$
Total Bilirubin + ALT	$\mu\text{mol/L}$	High	$1.5 \times \text{ULN}$ Total Bilirubin
			+
	U/L		$\geq 2 \times \text{ULN}$ ALT

Note: The following lab tests are being collected in this study but have not had PCI ranges defined: RBC Count, BUN, Creatinine, Direct Bilirubin and Total Protein. The maximum and minimum observed values will be reported as part of the lab summary tables and this is deemed sufficient to identify potentially extreme values which would then be investigated further if required.

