16.	All Subjects	CP_AE8 (Also see GSK2245035 TL7116958 idsfinal Listing 113)	Listing of Cytokine Release Syndrome Events	List all CRS events (even ones that map to the same CRS category but a lower grade)	SAC 1
17.	All Subjects	SAFE_L2 (Also see GSK2245035 TL7116958 idsfinal Listing 115)	Listing of worst case Cytokine Release Syndrome (CRS) Score by subject and dosing visit	Also add the allergen stratum to the Treatment when setting the page by line. Handle subjects who withdraw early like Subject PP in the example shell	SAC 1
18.	All Subjects	AE7 (Also see GSK2245035 TL7116958 idsfinal Listing 114)	Listing of Subject Numbers for Individual Cytokine Release Syndrome Events	ICH E3	SAC 1
19.	All Subjects	AE2	Listing of Relationship Between Cytokine Release Syndrome Event and associated AE System Organ Classes, Preferred Terms, and Verbatim Text	IDSL	SAC 1
Serious and Other Significant Adverse Events					
20.	All Subjects	CP_AE8a	Listing of Serious Adverse Events	ICH E3	FSP: SAC 1
21.	All Subjects	SAE Reasons	Listing of Reasons for Considering as a Serious Adverse Event	FDA Note: IDSL shell in development.	FSP: SAC 1

ICH : Listings					
No.	Population	IDSL / TST ID / Example Shell	Title	Programming Notes	Deliverable [Priority]
22.	All Subjects	CP_AE8	Listing of Adverse Events Leading to Withdrawal from Study / Permanent Discontinuation of Study Treatment	ICH E3	FSP: SAC 1
Hepatobiliary (Liver)					
23.	All Subjects	MH2	Listing of Medical Conditions for Subjects with Liver Stopping Events	IDSL	FSP: SAC 2
24.	All Subjects	SU2	Listing of Substance Use for Subjects with Liver Stopping Events	IDSL	FSP: SAC 2
Laboratory – Haematology					
25.	All Subjects	LB5	Listing of All Haematology Laboratory Data for Subjects with Values of Potential Clinical Importance	ICH E3	FSP: SAC 2
26.	All Subjects	CP_LB5	Listing of Haematology Laboratory Data Values of Potential Clinical Importance		FSP: SAC 2
Laboratory – Chemistry					
27.	All Subjects	LB5	Listing of All Chemistry Laboratory Data for Subjects with Values of Potential Clinical Importance	ICH E3	FSP: SAC 2
28.	All Subjects	CP_LB5	Listing of Chemistry Laboratory Data Values of Potential Clinical Importance		FSP: SAC 2
Laboratory – Urinalysis					

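### Unscheduled and out-of-window safety results are left out of every summary table, and for laboratory analytes without PCI limits the planned listings do not fill the gap

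*SAP*

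**What the plan says.** **Tables.** SAP 11.4.3 sets the rule for all displays: "Unscheduled visits will not be included in summary tables". The same section omits visits outside the protocol windows from summaries. SAP 11.2.1 adds that "items that fall outside of the window may be transferred using unscheduled timeslicing keys with the corresponding planned items containing no data", so a late planned sample can leave its planned cell empty.

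**Listings.** SAP 11.4.3 also promises that "All unscheduled visits will be included in listings".

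**Any-visit row.** SAP 11.5.1 describes a row counting subjects over all post-baseline visits: "Subjects having both High and Low values for Normal Ranges at any post-baseline visits for safety parameters" are to be counted in both directions. It does not say that unscheduled results count.

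**Analytes without PCI limits.** SAP 11.7.1 names five: RBC count, BUN, creatinine, direct bilirubin and total protein. For these it says: "The maximum and minimum observed values will be reported as part of the lab summary tables and this is deemed sufficient".

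**Schedule.** Protocol 7.1.2 says of the full laboratory panel: "Collect samples for laboratory assessments on DV1 and DV8". ECGs are also confined to DV1 and DV8. Both are done at an early-withdrawal visit that falls before follow-up. Protocol 7.1.3 plans haematology but no chemistry or ECG at the follow-up visits. Under Protocol Table 1, values judged clinically significantly abnormal "should be repeated until the values return to normal or baseline", and Protocol 7.4 lets safety time points be added during the study.

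**The concern.** Unscheduled samples are usually taken because something looked wrong, so they carry more safety information than their number suggests. A rule that keeps them out of by-visit rows is ordinary practice, because those rows need a common time point. A rule that also keeps them out of the any-visit and extreme-value summaries removes them from the displays whose purpose is to catch the worst value per subject.

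Two things are at stake. The first is the by-arm count of subjects with an emergent abnormality. The second is the check in SAP 11.7.1 for analytes without PCI limits: it is said to be enough to find extreme values, yet it sits in tables that cannot contain these results.

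**Working it through.** No power or sample-size figure is involved. The check traces an unscheduled result through the schedule, the tables and the listings.

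**1. Calendar** (weekly dosing from Day 1; Protocol 7.1.2 and 7.1.3)
- DV8 = 1 + 7 × 7 = Day 50, and DV8 24 h = Day 51.
- FUV3, 12 weeks after DV8, = 50 + 84 = Day 134.
- Planned post-baseline chemistry for a completer: DV1 24 h (Day 2), DV8 pre-dose (Day 50) and DV8 24 h (Day 51), so three time points.
- Days with no planned chemistry or ECG: Days 3 to 49, which is 49 − 3 + 1 = 47 days and spans doses 2 to 7; and Days 52 to 134, which is 134 − 52 + 1 = 83 days.
- If both DV8 samples were out of window, only Day 2 would remain in the chemistry tables.
- Haematology shares the first gap but is drawn again at the follow-up visits.

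**2. Tables** (SAP 11.13.7)
- Table 3.11 (emergent chemistry) is built on planned times. Its programming note gives the three time points above as examples. Table 3.13 (haematology) follows the same pattern.
- Table 3.10 gives absolute values at baseline only and change from baseline at later visits; Table 3.12 follows it. The extremes of observed values that SAP 11.7.1 relies on are therefore not specified after baseline even for planned visits.

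**3. Listings** (SAP 11.13.15)
- Listing 27 is titled "Listing of All Chemistry Laboratory Data for Subjects with Values of Potential Clinical Importance", and Listing 28 shows PCI values only. Listings 25 and 26 do the same for haematology. No full chemistry listing is planned, which does not match the promise in 11.4.3.

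**4. Where a result first seen at an unscheduled draw would appear**

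| Result | Summary tables | Listings |
|---|---|---|
| Analyte with a PCI limit, beyond it | Not counted | Listed (25–28) |
| Analyte with a PCI limit, outside normal range but within the limit | Not counted in 3.11 or 3.13 | Only if the subject has a PCI value on that panel |
| Creatinine, BUN or total protein, however extreme | Not counted, not in max/min | Listing 27 only if the subject has a PCI value on another chemistry test; never Listing 28 |
| QTc, PR or QRS beyond its limit | Not in 3.16 | Listed (32–33), with abnormal findings in 34 |

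**5. Scale.** Protocol 4.2 plans about 24 subjects per arm. One omitted subject changes an arm's percentage by 1/24 = 4.2 percentage points. The documents do not say how many unscheduled draws to expect, so no expected undercount can be calculated.

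**The case against.** A reader might infer that every chemistry and ECG value between doses 2 and 7 is lost, or that an extreme creatinine would appear in no output at all. The documents do not support either reading.

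- **Planned data exist in that period.** Early-withdrawal chemistry and ECG can fall there, and SAP 11.6.1 puts withdrawn subjects' planned data into the tables. Time points formally added under Protocol 7.4 could also count as planned.
- **Most extremes are listed.** ECG intervals and analytes with PCI limits reach the listings. Table 3.14 summarises liver monitoring and stopping events separately.
- **There is an adverse-event route.** Under Protocol 12.4.1 an abnormal result that the investigator judges clinically significant is an adverse event, and these are tabulated by arm and listed. The Safety Review Team also sees data in-stream.
- **The count is by subject.** A repeat after a planned post-baseline result that was already abnormal in the same direction adds nobody. Only a new abnormality does.
- **The five analytes differ.** RBC count belongs to haematology, which is also drawn at follow-up. Direct bilirubin is part of total bilirubin, which has a PCI limit. For planned draws, Table 3.11 also classifies results against normal ranges.
- **The rule says visits.** An extra draw at DV4 happens at a scheduled visit, so its status is arguable.

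All of this narrows the point, but it does not remove it. The adverse-event route depends on a judgement made result by result, whereas the max/min check exists to find extremes that still need looking into. On the last item, SAP 11.2.1 applies unscheduled keys to individual items, and Table 3.11 is organised by planned times, so a draw without a planned time would most naturally be left out.

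**Conclusion.** The concern holds in a limited form and should be corrected before database freeze.

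- For subjects who remain on treatment, an abnormality first seen at an unscheduled or out-of-window draw is absent from the by-arm any-visit counts in Tables 3.11 and 3.13. Each such subject is worth about 4 percentage points of an arm. That the counts will in fact be too low is possible but not shown.
- For analytes without PCI limits, in practice mainly creatinine, BUN and total protein, an extreme unscheduled value can be missing from every planned laboratory display. This requires that the subject has no other chemistry PCI value and that the result is not reported as an adverse event.
- ECG loses only its place in summary Table 3.16. No gap is shown for vital signs, which are measured at every dosing visit and have PCI listings.

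This rests on three assumptions: that the rule covers any result without a planned time, that the titles in the display list describe what the listings will contain, and that the mock shells, held in a separate document, add no exception. The efficacy analyses are not affected.

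**What to change.** 1. Amend SAP 11.4.3 so that unscheduled and out-of-window safety results stay out of by-visit rows but are included, by arm, in the any-visit post-baseline rows of Tables 3.11 and 3.13.
2. Add to Tables 3.10 and 3.12 a row with the absolute post-baseline maximum and minimum over all results, planned or not, so that the check in SAP 11.7.1 works as stated.
3. Add a full listing, for all subjects, of the analytes without PCI limits, so that the listings match the promise in 11.4.3.

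A worst-post-baseline row in ECG Table 3.16 is optional. Vital-sign Table 3.17 needs no change.

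The cost is one SAP sentence, programming notes for four tables and one extra listing. It uses data already collected.
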